8.2 Efficacy Endpoints

8.2.1 Primary efficacy endpoint

The primary endpoint is the proportion of HCW contracting an ARI necessitating workforce removal

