9.3 Criteria and procedures for participant withdrawal

9.3.1 Withdrawal of participants from study

Participants will be withdrawn from the study if any of the following conditions are met:

- The participant withdraws their consent
- The participant fails to return to the clinic (i.e., they are lost to follow-up or death)
- The site investigator or his/her designee believes that continuation in the study is no longer in the participant's best interests (which may be as a result of the occurrence of adverse events (AE) or clinically relevant laboratory results)
- The participant is unable to comply with the protocol, including completing required study treatments, procedures, tests and/or examinations
- The Sponsor reserve the right to terminate the entire study or any participants involvement at any time

Participants who prematurely discontinue investigational product will be encouraged to continue with the study visit schedule and assessments. For further information regarding Early Withdraw Visits refer to Section 10.4.

Those participants that cease the investigational product before the end of the study, but continue to be assessed for all other aspects of the study, will be regarded as members of the intention to treat (ITT) sample. All remaining study medication (including used and unused medication and packaging) will be collected.

In all cases, the reason and date of withdrawal from the study, or investigational product, will be completed in the source documentation and the CRF. If the withdrawal is due to an adverse event or a clinically significant laboratory result, the participant will be followed until the AE is resolved or is clinically stabilised. The AE or laboratory result must be recorded in the CRF.

If a participant tests positive to a clinical test (not part of the study) they will follow the hospital isolation protocol. The study Covid testing is done by measuring antibodies, which are not suitable for acute surveillance as it detects past infection. Results (positive or negative) will be returned to participant for their own information

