10.1.7 Patient daily symptom data

Following randomisation, the process will be explained to participants concerning their documentation of /response to daily SMS regarding any respiratory symptoms. These symptoms and/or condition related to the symptoms will be recorded as adverse events. Unclear or missing entries will be clarified with the participant and any correction annotated by site staff as appropriate. Annotations made by site staff will be clearly identified and initialled and dated.

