11.1 Enrolment and randomisation

Once all required screening assessments are completed and eligibility is confirmed, participants will be registered with the Sponsor. Upon approval of registration, participants will be assigned a unique participant number that will remain consistent for the duration of the study.

Participants who sign an informed consent form, but do not fulfil the inclusion/exclusion criteria, will not be allocated a participant identification number.

Participants will be randomised into one of the following two groups on a 1:1 ratio with 500 participants per group:

- Group 1 (WLC): OM85 7.0 mg will be given daily for three months from Month 3
- Group B (Initial Treatment): OM85 7.0 mg will be given daily for three months from Day 0

Please see the Study Reference Manual for randomisation instructions.

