13.2.1 Analysis sample

All participants randomised who receive at least one dose of study treatment will be included in the "intention-to-treat" group for statistical analyses.

Participants who complete the treatment period and take at least 80% of scheduled doses will be included in the "per protocol" group for statistical analyses.

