13.3.1 Primary efficacy endpoint

The primary endpoint, defined in Section 7.2.1, will be analysed 3 months after enrollment using data collected prior to the WLC group commencing treatment, by comparing between-group differences in rates of ARI that necessitated workforce removal. The primary analysis will be conducted using log-binomial regression on both the "intention-to-treat" and "per protocol" groups.

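### The per-protocol rule cannot classify wait-list workers at 3 months, and it lets dosing after the primary event decide membership in Group 2

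*Combined protocol and SAP*

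**What the plan says.** All references are to the combined protocol and SAP.

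- **Endpoint (8.2.1):** "The primary endpoint is the proportion of HCW contracting an ARI necessitating workforce removal".
- **Per-protocol rule (13.2.1):** "Participants who complete the treatment period and take at least 80% of scheduled doses will be included in the" per-protocol group. Neither this section nor 13.2.2 or 13.3.1 stops the dose count at the first ARI or exempts stops caused by one.
- **Use of the set (13.3.1):** the primary endpoint is analysed at 3 months, "using data collected prior to the WLC group commencing treatment", on both the ITT and the per-protocol sets. Neither set is ranked above the other.
- **Who is dosing then (11.1):** Group 2 takes capsules from Day 0. For the controls, "Group 1 (WLC): OM85 7.0 mg will be given daily for three months from Month 3".
- **Stopping product but staying (9.3.1):** "Those participants that cease the investigational product before the end of the study, but continue to be assessed" are counted in the ITT sample. The CRF records "the reason and date of withdrawal from the study, or investigational product", and an adverse event is one of the reasons foreseen.
- **Respiratory symptoms (10.1.7):** "These symptoms and/or condition related to the symptoms will be recorded as adverse events".
- **ITT set (13.2.1):** "All participants randomised who receive at least one dose of study treatment will be included in the" ITT group.

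**The concern.** The 3-month window coincides with Group 2's dosing period and precedes the controls' first dose. A rule based on treatment completion and doses taken therefore has two faults there.

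First, a wait-list worker has no treatment period to complete and no doses to count before Month 3, so 13.2.1 does not say who among the controls is per protocol. Some control definition has to be supplied before the analysis can be run.

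Second, the Group 2 count runs past the outcome. A Group 2 worker who has the primary event, gives up the capsules for good and stays in follow-up is a case in ITT but is removed from per protocol. A wait-list worker with the same illness has no doses to give up. A repair that only defines controls would leave this in place: cases would be removed from one arm because they are cases, and the per-protocol risk ratio would fall below 1 even with an inert drug. Since 13.3.1 names per protocol as one of two sets for the primary analysis, that result could be read as confirmation.

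**Working it through.** **The plan's own figure.** Section 13.2 assumes 20% in Group 1 and 13.5% in Group 2, with 500 per group, for 80% power. A pooled two-sided two-proportion calculation gives 78.7%. For 20% against 15% with 1000 per group it gives 83.8%. The stated power is broadly reproduced. Only the 20% is carried forward.

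**Inputs**

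- p = 0.20 in both arms (13.2), taken as the 3-month risk of the primary event, with no drug effect. The 3-month reading is an assumption.
- 90 scheduled doses, from daily dosing to Day 90 (11.1, Appendix 1). The 80% threshold is 72 doses, so 90 - 72 = 18 may be missed.
- Constant hazard of ARI, all controls retained, and full adherence otherwise (assumptions).
- f = share of Group 2 cases who stop OM85 for good at the ARI but stay in the study. The documents give no value.

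**Cases open to exclusion, e.** If only the dose threshold binds, the ARI must come before day 72: e = 1 - (1 - 0.20)^(72/90) = 0.1635. If any permanent stop counts as not completing treatment, e = p = 0.20.

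**Group 2 per-protocol risk:** r = (p - f·e)/(1 - f·e). For f = 0.10 under the completion rule, (0.20 - 0.02)/(1 - 0.02) = 0.1837, and the risk ratio is 0.1837/0.20 = 0.92.

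**Chance of a significant per-protocol result favouring OM85:** Φ[(0.20 - r - 1.96·SE0)/SE1], where SE0 is pooled, SE1 is unpooled and Group 2 has n(1 - f·e) workers. For the same case with n = 1000: SE0 = 0.0177, SE1 = 0.0177, (0.0163 - 0.0347)/0.0177 = -1.04, giving 15.0%. The nominal value is 2.5%.

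Each cell shows the dose rule, then the completion rule.

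| f | Group 2 risk | Null risk ratio | Excluded per 1000 | Chance, 500 per group | Chance, 1000 per group |
|---|---|---|---|---|---|
| 0 | 0.2000 / 0.2000 | 1.00 / 1.00 | 0 / 0 | 2.5% / 2.5% | 2.5% / 2.5% |
| 1% | 0.1987 / 0.1984 | 0.99 / 0.99 | 2 / 2 | 2.8% / 2.9% | 3.0% / 3.1% |
| 2% | 0.1974 / 0.1968 | 0.99 / 0.98 | 3 / 4 | 3.2% / 3.3% | 3.5% / 3.8% |
| 5% | 0.1934 / 0.1919 | 0.97 / 0.96 | 8 / 10 | 4.5% / 5.1% | 5.6% / 6.6% |
| 10% | 0.1867 / 0.1837 | 0.93 / 0.92 | 16 / 20 | 7.6% / 9.5% | 11.3% / 15.0% |

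A Wald test on the log risk ratio, closer to the planned log-binomial model, agrees within 0.5 percentage points.

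**Lower risk** (f = 10%, 1000 per group): at p = 0.10 the risk ratio is 0.93 / 0.91 and the chance 8.0% / 10.2%; at p = 0.05 they are 0.92 / 0.90 and 5.9% / 7.2%.

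**Pauses.** A worker who misses no more than 18 doses and then completes treatment stays in the set, so there is no bias.

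**Leaving the study altogether.** Read literally, leavers in both arms fail the rule. If 25% of cases in each arm leave, Group 1 risk is (0.20 - 0.05)/(1 - 0.05) = 0.1579. Group 2 is 0.1659 (dose rule) or 0.1579 (completion rule). The risk ratio is 1.05 or 1.00, so there is no lean towards OM85.

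**The case against.** The arithmetic is not in dispute. The case against is about how much it describes this trial.

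- **The lean depends on a repair not yet made.** As written, controls have no per-protocol membership, so there is no per-protocol comparison to be biased. This stands. The two faults sit in the same sentence and should be corrected together.
- **Nothing says an ARI ends dosing.** OM85 is a daily oral capsule (11.2) that can be taken while off work, and no medicine is prohibited (11.5). The unscheduled ARI visit (10.2, Appendix 1) does not list drug collection, which is scheduled at treatment cessation. Section 10.1.7 shows only that symptoms are logged as adverse events. This also stands: f could be close to zero, where the risk ratio is 0.98-1.00.
- **The one passage linking an ARI to discontinuation (10.3) concerns leaving the study**, and that route gives no lean towards OM85. This is correct. The route that does is a subset of the general stop-but-stay provision in 9.3.1, which is foreseen but not quantified.
- **A completer set with an 80% threshold is a common convention, reported here beside ITT.** That is fair. But here only one arm is being dosed during the comparison, and 13.3.1 does not call the set supportive.
- **The remedy has its own bias**, which can exceed the one it removes. This is true and is costed under the fix.

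A reader might go further and infer that the trial's primary result is biased, or that its false-positive rate is badly inflated. At f = 25% the same formula gives a risk ratio of 0.83-0.79. Nothing in the documents supports so large an f. The error rates apply to the per-protocol result alone, since stop-but-stay workers remain cases in ITT.

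**Conclusion.** The point holds as a minor one. The per-protocol definition cannot be applied to controls at 3 months, and in Group 2 it allows the outcome to decide membership. Both follow from the text.

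The direction of the second fault is clear once controls are defined: towards OM85. Its size is not known. At 20% risk with no drug effect, the illustrative risk ratio is 1.00 at f = 0, 0.98-0.99 at 1-2%, 0.96-0.97 at 5% and 0.92-0.93 at 10%. These figures rest on constant hazard, 90 scheduled doses, retained controls and full adherence otherwise.

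The documents do not support saying that workers with an ARI are routinely taken off OM85, that workers who leave the study create this lean, or that the ITT comparison suffers from it. The ITT set has a separate weakness: its one-dose condition omits wait-list workers who leave before Month 3. Nothing is claimed here about the month-1 interim.

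**What to change.** 1. In 13.2.1, for the 3-month analysis, define per-protocol membership in both arms over one window, ending at the first ARI necessitating workforce removal or at Day 90, whichever is earlier. Group 2: still on treatment at that point, with 80% or more of the doses scheduled to it. Group 1: followed to that point without OM85.
2. In 13.3.1, state that the per-protocol result is supportive of an analysis of all randomised participants.

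**Cost.** Two sentences and one programming rule in 13.2.1, and one sentence in 13.3.1, with no extra visits or participants. Stop dates and reasons are recorded under 9.3.1 and compliance under 11.4. A dose count to the ARI date would use the pack returns that 11.4 requests at each visit, although 10.2 does not list them for the unscheduled visit.

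**Downside.** Cases are judged over fewer days than non-cases, so fewer of them fail. Suppose a share q of Group 2 non-cases stop for unrelated reasons at a constant hazard, and a smaller share c of cases do so before their ARI. Then Group 2 risk = p(1 - c)/[p(1 - c) + (1 - p)(1 - q)]. For q = 5%, 10% and 15%, c is 2.4%, 4.9% and 7.4%, the risk is 0.2043, 0.2090 and 0.2140, and the null risk ratio is about 1.02, 1.045 and 1.07. The upper bounds, with no case excluded, are 1.04, 1.09 and 1.14.

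On the log scale this equals the bias removed when f is about 3%, 5-6.5% and 8-10% respectively. Below those values the new rule lies further from the null than the present one, but against OM85 rather than for it.

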13.2.2 Statistical analyses

The *interim analysis*, undertaken at month 1 on both the "intention-to-treat" and "per protocol" groups, will examine the primary outcome: if the treatment difference is statistically significant in favour of OM85 the DSMB will consider immediately switching WLC participants to OM85.

Between-group differences in the primary outcome at 3 months will be assessed using log-binomial regression. Secondary outcomes measured to follow-up cessation will be assessed using mixed-effects models with group and stage (treatment/follow-up) (main effects and interaction) as fixed effects and HCW as random effect. Time-to-ARI analyses will use the log-rank test. Analyses will be undertaken on both the "intention-to-treat" and "per protocol" groups.

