Serious Adverse Event Reporting Children's Health and Environment Program, (CHEP)
Child Health Research Centre
[contact]

2. Investigator Signature Page

Reducing acute severe respiratory events in health care workers during the Covid-19 pandemic with OM85

I confirm that I have read **Protocol Version 2.0 dated 12th June 2020**. As the site investigator, I understand it, and I agree to adhere to the study conduct requirements and agree to conduct this protocol in accordance with International Conference on Harmonization Good Clinical Practice E6 (ICH-GCP), the Declaration of Helsinki, the United States (US) Food and Drug Administration (FDA), and local regulations and guidelines. I agree to report all information or data in accordance with the protocol and in particular I agree to report any serious adverse events. I will accept the monitors, auditors and regulatory inspector's oversight of the study. I will promptly submit the protocol to the applicable ethical review board.

Chief investigator signature

[name] [name]

Chief investigator printed name

Date

This page has been left blank intentionally

3. Synopsis of Protocol

Title	A phase 3, multi-centre study testing the reduction of acute severe respiratory events in health care workers during the Covid-19 pandemic with OM85
Clinical phase	Phase Three
Protocol number	BV-2020/19
Principal Investigators	[name] [name] [name] Assoc [name] [name] [name] [name] Assoc [name] [name] [name]
Statistical consultant	[name]
Study design	Parallel group, Wait-list design, with treatment delayed for 3 months Participants will be randomized on a 1:1 ratio with 500 participants per group in Australia and 500 per group in the UK. Group 1: Wait-list control. One capsule OM85 (7.0 mg) will be given daily for 3 months, commencing in Month 3, with 3 months follow-up off treatment. Group 2: Initial treatment. One capsule OM85 (7.0 mg) will be given daily for 3 months, commencing on day 0, with 3 months follow-up off treatment.
Accrual objective	2000 Health Care Workers (HCW):- 1000 from Brisbane Hospitals 1000 from UK Hospitals

Accrual period	4 weeks
Study duration	12 months
Countries	Australia, United Kingdom
Sites	Queensland Children’s Hospital, Brisbane (Site Investigator: [name]) Imperial College Hospital, London (Site Investigator: [name]) Prince Alexandra Hospital, Brisbane (Site Investigator: [name]) Princess Charles Hospital, Brisbane (Site Investigator: Assoc [name])

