13.2 Sample size calculations

There are no data in the literature on use of OM85 for the primary prevention of ARI, in relation to COV. However, 20% of Italy's HCW are infected with COV¹. If we assume 20% infection in Gp 1, then with 500 HCW in each group we will be able to detect a reduction in ARI in Gp 2 by 32.5% (to 13.5%) with 80% power ($\alpha=0.05$). Combined with 1000 UK-recruited HCW, we will be able to detect a 25% reduction (80% power, $\alpha=0.05$).

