13.3 Study endpoint assessments

Study endpoint analyses will be conducted 3 months after enrolment and at completion of the study, with an interim analysis planned at month 1.

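### The month-1 interim test of the primary outcome has no significance level, boundary or workable analysis set; using 0.05 at both looks can raise the one-sided false-benefit rate from 2.5% to about 4.5%

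*Combined protocol and SAP*

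**What the plan says.** Section 13.2.2 plans an interim analysis of the primary outcome at month 1, in both the intention-to-treat and per-protocol groups, and adds: "if the treatment difference is statistically significant in favour of OM85 the DSMB will consider immediately switching WLC participants to OM85". Section 13.3 repeats only the timing ("with an interim analysis planned at month 1").

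The final test is a log-binomial regression at 3 months. Section 13.3.1 bases it on comparison "using data collected prior to the WLC group commencing treatment".

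The only significance level is the 0.05 in section 13.2, where it supports the statements "with 500 HCW in each group we will be able to detect a reduction in ARI in Gp 2 by 32.5% (to 13.5"%) and "Combined with 1000 UK-recruited HCW, we will be able to detect a 25% reduction". Whether it is one- or two-sided is not stated, and it is not assigned to either look.

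Section 13.2.1 defines the intention-to-treat group as "All participants randomised who receive at least one dose of study treatment" and the per-protocol group as "Participants who complete the treatment period and take at least 80% of scheduled doses".

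The stopping rules (synopsis and section 8.3) cover treatment-related death, sponsor decision and DSMB safety advice. Section 15.5 covers DSMB review of safety, data quality and trial conduct. Neither contains an efficacy boundary.

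**The concern.** The primary outcome is tested twice and no rule shares the error between the looks. A reader who takes statistically significant to mean p<0.05 will spend the full level at month 1 and again at month 3.

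The interim is also tied to a possible early start of OM85 in the controls. Section 13.3.1 describes the scheduled month-3 start and is silent on an earlier one. If its restriction to untreated control time is carried over, an immediate switch would turn the month-1 data into the primary data and end the comparison that could correct a chance result. If it is not carried over, the month-3 data by assigned group remain primary. The plan leaves this open.

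Whoever runs the interim must therefore choose the level, the analysis set and the status of the result. Such choices lose credibility once data have been seen.

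**Working it through.** **Inputs.** Control risk 20%; 500 per group (Australia) or 1000 per group (combined); level 0.05 (section 13.2). Looks at months 1 and 3 (section 13.3). "Accrual period 4 weeks" (synopsis). Assumptions: two-sided 0.05 (0.025 for benefit, critical value 1.96) at both looks, and a constant hazard.

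**1. The plan's own figures.** Power = Φ{[|p1−p2|√n − 1.96√(2p̄(1−p̄))] / √[p1(1−p1)+p2(1−p2)]}.
- 500 per group, 20% vs 13.5%: (1.4534 − 1.0351)/0.5261 = 0.795, power 78.7%.
- 1000 per group, 20% vs 15%: (1.5811 − 1.0532)/0.5362 = 0.985, power 83.8%.

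Both are near the stated 80%. A one-sided 0.05 would give 90.3% in the second case, so two-sided is the better reading. No interim adjustment is needed to reach these figures.

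**2. Information at month 1.** Month-1 control risk is 1 − 0.8^(1/3) = 7.17%. Under no effect, the information on the log risk ratio is proportional to p/(1−p): (0.0717/0.9283)/(0.20/0.80) = 0.31. If month 1 ran from first enrolment with uniform 28-day accrual, mean exposure at day 30 would be 16 days and the information about 0.16. I use 1/3 and 1/6 as the range.

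**3. False-benefit rate under no effect.** Z1 and Z3 are bivariate normal with correlation √t, where t is the month-1 information.

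(a) *The crossing is the finding, or the switch is immediate and the data stop there:* P(Z1>1.96 or Z3>1.96) = 0.05 − P(both).
- t = 1/3: 0.05 − 0.0058 = 4.4%
- t = 0.31: 0.05 − 0.0055 = 4.5%
- t = 1/6: 0.05 − 0.0035 = 4.7%

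(b) *Every crossing leads to a switch at month s and the test uses data to s:* P(Z1 and Zs both >1.96) + 0.025 − P(Z1 and Z3 both >1.96), with t = 1/3 and correlation √(1/s) between Z1 and Zs.
- s = 1.25: 0.0146 + 0.025 − 0.0058 = 3.4%
- s = 1.5: 0.0115 + 0.025 − 0.0058 = 3.1%
- s = 2: 0.0084 + 0.025 − 0.0058 = 2.8%

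Outside that window the rate is 3.7% at month 1.1 and 2.6% at month 2.5.

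(c) *Only a month-3 comparison by assigned group counts:* 2.5%, whether or not controls switch.

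Simulation (400,000 trials per scenario, binomial counts) agrees, with 4.4% for (a) at 1000 per group. Under no effect and t = 1/3, 77% of month-1 crossings would not be significant for benefit at month 3 (1 − 0.0058/0.025).

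**4. What a p<0.05 crossing looks like under the planned effect** (simulated; month 1 counted per participant).

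| | 1000/group, 20% vs 15% | 500/group, 20% vs 13.5% |
|---|---|---|
| Chance of crossing | 41% | 36% |
| Mean events at crossing, control vs OM85 | 77 vs 48 | 40 vs 20 |
| Median RR at crossing | 0.64 | 0.51 |
| True month-1 RR | 0.74 | 0.66 |

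**5. The interim sets.** Treatment lasts 3 months, so nobody can have completed it at month 1 and the per-protocol set is empty. Group 1 has its first dose at month 3, so a set that requires one dose has no controls at month 1.

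**The case against.** The DSMB is asked only to consider a switch, so a crossing binds nobody, whereas case (b) assumes that every crossing leads to one. Section 13.3.1 places the primary analysis at 3 months and never mentions an early switch. If the month-3 comparison by assigned group is decisive, the error is the intended 2.5%. This stands, and it is why the inflation is conditional.

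A reader might infer that the rate is 2.5% only when no switch follows. The documents do not support that. A switch followed by a month-3 analysis by assigned group keeps 2.5%, while a crossing claimed as the result without any switch gives about 4.5%. A reader might also infer that section 13.3.1 makes the month-1 data primary after a switch. That is one reading of a sentence written for the scheduled start.

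Month 1 is most naturally counted per participant, since section 13.3 sets it beside an analysis at 3 months after enrolment. The 4.7% end then applies only if few events fall early.

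The loss of power is small. If each crossing led to a switch at month 1.25, overall power at 1000 per group would be 81.5% against 83.8%.

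The dose-based definition of intention-to-treat also affects the month-3 analysis and needs correcting there as well. That does not make the interim workable.

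None of this supplies the missing level.

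**Conclusion.** The point holds. The plan tests its primary outcome at month 1, attaches a possible switch of controls to significance, and gives no interim level, boundary or adjusted final level. With two-sided 0.05 assumed at both looks, the one-sided false-benefit rate is about 4.5% against an intended 2.5% when the crossing is the finding, or when an immediate switch ends the primary data. The intermediate values of 2.8% to 3.4% apply only to switches at about months 1.25 to 2 with truncated data. They are not general bounds. The intended rate holds only if the month-3 comparison by assigned group alone is decisive, and the plan does not say so.

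Independently of these figures, the interim cannot be run in the sets that section 13.2.1 defines. Both matters need settling before month 1.

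**What to change.** Before month 1, amend sections 13.2.2 and 13.3 and the DSMB charter as follows.

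- State one interim efficacy boundary and the matching final level that together hold two-sided 0.05. Options are two-sided p<0.001 with a final level of about 0.0495; an O'Brien-Fleming-type spending function evaluated at the observed information (about 0.0002 then 0.0499 at information 1/3); or a Pocock-type level of about 0.027 at both looks. The choice is for the sponsor and DSMB.
- Apply the boundary once, to all randomised participants by assigned group, and drop the month-1 per-protocol analysis.
- State that month 1 is counted per participant from enrolment.
- State which data give the primary result if controls start OM85 early, and report a boundary-adjusted estimate.

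Whether and when to switch participants stays with the DSMB.

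**Cost.** The change is to wording, but each boundary has a price under the planned effect.
- *p<0.001:* the chance of crossing at month 1 falls from about 41% to 5% (1000 per group) and from 36% to 3% (500 per group). A crossing then exaggerates the effect more, with median RR about 0.52 and 0.37. Final power is almost unchanged: 83.7% against 83.8%, and 78.6% either way.
- *Pocock-type:* the chance of crossing is about 32% and 27%, but overall power is about 79% and 73%, against 84% and 79% for a single month-3 test at 0.05.

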9.4 Replacement of participants

Participants who withdraw consent or who discontinue the study for any reason will not be replaced.

10. Study procedures

The study procedures are listed in the Schedule of Assessments and Procedures in Appendix 1.

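### The primary log-binomial analysis has no rule for workers who leave before Month 3 without an ARI, and the dosing-based ITT set treats such leavers differently by arm

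*Combined protocol and SAP*

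**What the plan says.** The endpoint is binary. Section 8.2.1: "The primary endpoint is the proportion of HCW contracting an ARI necessitating workforce removal". Section 13.2.2 gives the method: "Between-group differences in the primary outcome at 3 months will be assessed using log-binomial regression". Section 13.3.1 limits it to the first three months, "using data collected prior to the WLC group commencing treatment".

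Two places define the ITT set. Section 13.2.1: "All participants randomised who receive at least one dose of study treatment will be included in the" intention-to-treat group. Section 9.3.1 says of those who stop the product early that workers who stop "but continue to be assessed for all other aspects of the study, will be regarded as members of the intention to treat (ITT) sample". Section 11.1 fixes when Group 1 is first dosed: "Group 1 (WLC): OM85 7.0 mg will be given daily for three months from Month 3".

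Section 9.3.1 lists the routes off study, including withdrawn consent, failure to return, investigator decision and inability to comply (which covers not completing treatment). Section 9.4 adds: "Participants who withdraw consent or who discontinue the study for any reason will not be replaced". Section 13.2 gives no dropout rate or allowance. The nearest provisions on missing data are queries on diary entries (10.1.7), telephone calls (10.1.8) and an early withdrawal visit (10.3). None of them assigns a primary outcome to a worker who has left.

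**The concern.** A log-binomial model has no term for partial follow-up. A worker who leaves on Day 30 without an ARI must be scored 'no ARI', dropped, or imputed, and the plan does not say which. The choice would then be made with the data in hand. The log-rank analysis of time to ARI can censor such a worker, but it is secondary.

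The wording of the analysis set adds a second problem. Membership under 13.2.1 depends on having had a dose, and before Month 3 only Group 2 has had one. Taken literally, the same early departure removes a Group 1 worker from the analysis and leaves a Group 2 worker in.

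Unequal leaving is plausible. Workers know their arm, there is no placebo, and before Month 3 only Group 2 has a treatment to comply with. At stake is the size of the primary risk ratio and, in some circumstances, the significance decision.

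**Working it through.** **Inputs from the documents.** Control risk 20%; 13.5% in Group 2 with 500 per group (Australia); a 25% reduction, to 15%, with 1000 per group (both countries); 80% power, α = 0.05 (all 13.2). Two-sided testing is assumed, because sidedness is not stated.

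**Assumptions.** Leaving 5% to 15% per arm, uniform over 90 days and unrelated to ARI risk; constant hazard; no stratification covariates.

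**1. The plan's own figures.** Pooled two-proportion power = Φ[(Δ − 1.96·SE₀)/SE₁].
- 20% vs 13.5%, 500 per group: SE₀ = √(2 × 0.1675 × 0.8325/500) = 0.02362; SE₁ = √((0.16 + 0.1168)/500) = 0.02353; power = Φ(0.795) = 78.7%.
- 20% vs 15%, 1000 per group: SE₀ = 0.01699; SE₁ = 0.01696; power = Φ(0.985) = 83.8%.

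The sample-size statement is broadly reproduced, so its inputs are used below.

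**2. Risk recorded before leaving.** The probability of an ARI before a uniform leaving time is q = 1 − 0.2/(−ln 0.8) = 1 − 0.2/0.2231 = 0.1037. The SE of the difference with no true effect is √(2 × 0.2 × 0.8/1000) = 1.79 points. The one-sided false-benefit rate is Φ(−1.96 + shift towards OM85 in SE).

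**3. Literal 13.2.1 set, equal 10% leaving, no true effect.** Group 1 leavers are out, so the Group 1 risk is 20.0%. Group 2 leavers stay in, scored 'no ARI' unless an ARI came first: 0.90 × 0.20 + 0.10 × 0.1037 = 19.04%. The shift is 0.96 points = 0.54 SE towards OM85, and the false-benefit rate is Φ(−1.42) = 7.8%. At equal 5% leaving it is 0.48 points, 0.27 SE and 4.5%. If all 10% left near Day 0, the shift would be 2.0 points = 1.12 SE and the rate about 20%.

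**4. All randomised workers kept, no true effect.** With leaving fraction d:
- 'No ARI' risk = (1 − d)0.2 + dq.
- Risk after dropping event-free leavers = [(1 − d)0.2 + dq]/[(1 − d) + dq].

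| Leaving, Group 1 vs Group 2 | 'No ARI': risks | Shift | Dropping: risks | Shift |
|---|---|---|---|---|
| 10% vs 10% | 19.04% vs 19.04% | 0 | 20.91% vs 20.91% | 0 |
| 10% vs 5% | 19.04% vs 19.52% | 0.27 SE against OM85 | 20.91% vs 20.43% | 0.27 SE towards OM85 |
| 15% vs 5% | 18.56% vs 19.52% | 0.54 SE against OM85 | 21.44% vs 20.43% | 0.56 SE towards OM85 |

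At 15% vs 5%, dropping gives a false-benefit rate of 8.1%. With the imbalance reversed (5% vs 15%) the directions swap, and 'no ARI' scoring gives 7.8%. Neither rule is safe in both directions.

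**5. Can the decision change between these two handlings?** This step uses a Wald test on the log risk ratio, SE = √(1/x₁ − 1/n₁ + 1/x₂ − 1/n₂), with 200 Group 1 ARIs among 1000 and leavers having no recorded ARI.
- Equal dropout of 5%, 10% or 20%: the two handlings never disagree at p < 0.05. For 200 vs 150 ARIs at 10%, both give p = 0.003.
- 5% vs 10%: they disagree for 157 to 166 Group 2 ARIs. At 160, p = 0.020 ('no ARI') and p = 0.076 (dropping).
- Design effect, 200 vs 150: at 5% vs 15%, p = 0.003 and p = 0.069. The smallest Group 2 dropout that flips the result is 9.5% against 0%, 14% against 5%, and 18.5% against 10% in Group 1, which is about 9 points of imbalance.

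**The case against.** A reader might infer that 9.3.1 and 13.2.1 prescribe opposite treatments of leavers. They do not. Section 9.3.1 speaks of product-stoppers who remain under assessment and is silent on workers who leave the study. Section 13.2.1 sets membership by dosing. That one section means dropping and the other means 'no ARI' is inference.

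A reader might also infer that the gap is in itself enough to reverse the primary result. Step 5 does not support that. On the all-randomised set the two handlings agree at equal dropout. Nor do the discontinuation figures in 6.3 (5/142 on OM85, 9/131 on placebo) supply a leaver rate. They count people stopping the product, in a study of COPD or chronic bronchitis, and 9.3.1 encourages product-stoppers here to stay on the visit schedule.

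The literal reading of 13.2.1 may not be intended. At the month 1 interim, which 13.2.2 also runs on the ITT set, no Group 1 worker has had a dose, so the definition would empty that arm. This suggests loose drafting, but it is also a reason to change the words. Daily SMS, queries and the early withdrawal visit should limit missing data. They do not score what happens after a worker has gone.

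What stands is the missing rule, the unaligned ITT wording, and the asymmetry in 13.2.1 as written.

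**Conclusion.** The concern holds as a gap in the primary analysis that should be closed before the data are seen. The stronger part is the dosing condition. With Group 2 leavers scored 'no ARI', it favours OM85 by about 0.5 SE even at equal 10% leaving. On the all-randomised set, the two simple handlings part only under unequal dropout, with opposite biases of about 0.27 SE each at 10% vs 5% and about 0.55 SE each at 15% vs 5%. Between those two handlings, the decision can flip only with unequal dropout, together with either a borderline result or about 9 points of imbalance at the design effect.

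Every dropout rate here is an assumption, as are uniform leaving and leaving unrelated to illness. The documents do not support a statement that a flip is likely.

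**What to change.** - **13.2.1:** define the ITT set as all randomised workers in their allocated group, with no dosing condition. Without this change, imputation would not reach Group 1 leavers.
- **9.3.1:** remove continued assessment as a condition of ITT membership, so that the two sections agree.
- **13.3.1:** keep log-binomial regression. Count any ARI with workforce removal before leaving as an event. For a worker who leaves event-free before Day 90, multiply impute the outcome over the remaining days from the observed hazard by arm and randomisation stratum.
- **Sensitivity:** add a tipping-point analysis that varies the event risk of leavers. It is needed because imputation from the observed hazard does not remove bias if workers leave because they are becoming ill.

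The cost is wording, a little more analysis work and a slightly wider confidence interval than single scoring would give. No new data or participants are needed.
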